3.2 Exclusion Criteria

1. Patients with previous or concurrent malignancy, excluding non-melanotic skin cancer. Malignancies treated and without recurrence or symptoms of recurrence within the last 3 years are acceptable.
2. Patients with evidence of distant metastatic disease.
3. Patients who have had chemotherapy, biologic or radiotherapy within 6 months of biopsy.
4. Patient usage of herbal supplements or alternative medications not approved by the FDA within 1 week of starting study drug. LEAG or related ginseng products, and combination products containing ginseng should be discontinued within 6 weeks of starting study drug.

5. Patients with a history of allergic reactions attributed to compounds of similar chemical or biologic composition to LEAG, including other products claiming to contain ginseng in any form.
6. Patients with a history of a chronic inflammatory process, including, but not limited to, rheumatoid arthritis and lupus. This includes patients on concurrent chronic systemic steroids or anti-inflammatory medications.
7. The subject has active bleeding (i.e. gastrointestinal ulcer with bleeding) or a pathological condition that carries a high risk of bleeding, in the investigator's opinion.
8. Patients with any swallowing dysfunction leading to difficulty taking the investigational therapy are ineligible for the study.
9. Uncontrolled intercurrent illness including, but not limited to, ongoing or active infection, symptomatic congestive heart failure, unstable angina pectoris, cardiac arrhythmia, or psychiatric illness/social situations that would limit compliance with study requirements. HIV-positive patients on combination antiretroviral therapy are ineligible because of the potential for pharmacokinetic interactions with LEAG. Appropriate studies will be undertaken in patients receiving combination antiretroviral therapy when indicated.
10. Patients with poorly controlled diabetes (control indicated with HbA1c \leq 8.5 within past 60 days or documented fasting blood glucose $<$ 140 mg/dl for three consecutive days). Known diabetics who have experienced episodes of symptomatic hypoglycemia in the last 6 months are also considered poorly controlled and will be excluded from study participation.
11. Patients with uncontrolled hypertension (SBP $>$ 140 mmHg or DBP $>$ 90 mmHG). Should a subject's blood pressure on initial presentation fall above defined parameters for hypertension two additional blood pressure measurements will be performed at least 15 minutes apart. The initial blood pressure and two additional measurements will be averaged. If the average of the three measurements remains above the defined parameters for hypertension, the patient will be excluded. If the average of the three measurements falls below the defined parameters for hypertension, the patient will be considered to meet eligibility.
12. Pregnant or breast feeding women. Women must be willing to use birth control throughout study duration.
13. Patients on other investigational medications or having been treated with an investigational agent within 6 weeks prior to biopsy.
14. Patients currently receiving coumadin therapy or who have been treated with coumadin within the 2 weeks prior to biopsy.
15. Patients taking monoamine oxidase inhibitors.

3.3 Inclusion of Women and Minorities

Women and members of all races and ethnic groups are eligible for this trial.

4.0 REGISTRATION AND ENROLLMENT PROCEDURES

4.1 General Guidelines

To be eligible for registration to this study, the patient must meet each inclusion criteria listed on the eligibility checklist and none of the exclusion criteria should apply. To be registered, the patient must have the ability to understand and the willingness to sign the written informed consent.

4.2 Registration Process

- Contact the Clinical Trials Office (CTO) at [contact] with patient information: name, physician, and diagnosis.
- CTO staff will screen patients' charts for eligibility. The CTO must have the following information, at minimum, to determine eligibility: past medical history information, diagnostic biopsy report, radiologic exams, and staging information.
- If the patient is eligible following chart review: CTO staff will meet with patient to review the Informed Consent Form and proceed in obtaining written consent.

4.3 Criteria for Enrollment

- Confirmation that patient has met all of the Inclusion Criteria and none of the Exclusion Criteria.
- Patient has voluntarily signed informed consent document.

5.0 TREATMENT PLAN

5.1 Screening Procedures

- 5.1.1 History and physical reviewed and recorded, including performance status.
- 5.1.2 Concomitant medications reviewed and recorded.
- 5.1.3 Vital signs reviewed and recorded.
- 5.1.4 Inclusion and exclusion criteria will be reviewed.
- 5.1.5 Review and record available HbA1c status (within past 60 days) or fasting blood glucose values (three consecutive days below 140 mg/dl)
- 5.1.6 Informed consent process
- 5.1.7 Pregnancy test, if required

5.2 Study Visit 1

- 5.2.1 Obtain tissue blocks for immunohistochemistry from core biopsy

- Proliferation Markers: immunohistochemistry for ER, PR, Ki67, cyclin D1, Cox-2, and angiotensin 2.
- Cytotoxicity Markers: cyclin D2 and TUNEL
- Angiogenesis Markers: angiotensin 2

5.2.2 Fasting lab work will be obtained.

Serum for levels of gRc and gRh2, inflammatory mediator proteomic panel (IL1b, IL6, IL8, MCP-1, TNFa, HGF, NGFb, Insulin, and Leptin), pregnancy test (if not already done at screening visit) if woman is of child-bearing potential, HOMA index, leptin, ghrelin, and adiponectin.

5.2.3 Questionnaires will be completed

Dietary, Tecumseh and Minnesota Activity Questionnaires

A. Tecumseh and Minnesota Occupational and Leisure Time Activity

Questionnaires: Both occupational and leisure time exercise exposure for the prior 12 months will be measured by the Tecumseh and Minnesota occupational and leisure time activity questionnaires. The validity and reliability of the Tecumseh Occupational Physical Activity Questionnaire (43) has been documented by Ainsworth (44, 45) (Appendix A). Leisure time physical activity will be measured by the Minnesota Leisure Time Physical Activity Questionnaire (Appendix B) which has also been previously tested for validity and reliability and is a well-accepted measurement tool (43). Of note, the use of the Tecumseh and Minnesota Occupational and Leisure Time Surveys allow for calculation of energy expenditure. Specifically, each activity recorded on the survey will be assigned a calculated metabolic equivalent (MET) value based on the published compendium of physical activity (46). This MET value will be multiplied by the number of hours spent in each activity per week (i.e. METs x hrs/wk). This variable (METs x hrs/wk) will then be analyzed for the study group as a continuous variable and in quartiles.

B. National Cancer Institute Dietary History Questionnaire: The current proposal will utilize the Dietary History Questionnaire (DHQ) developed by the Risk Factor Monitoring and Methods Branch (RFMMB) of the National Cancer Institute. The *Eating at America's Table Study* conducted by the RFMMB compared their new DHQ with the previous standard Block and Willet food frequency questionnaires (FFQs). The DHQ performed best of all in a randomized sample of 1,640 men and women (47). The DHQ is a self-administered questionnaire that represents a refinement over the RFMMB Block FFQ, with

improved comprehension across various economic and ethnic groups and increased attention to dietary constituents of interest in disease prevention: fiber, energy, carotenoids and vitamin A, E and C (Appendix C). The questionnaire will be entered into an ASCII text file and analyzed using Diet*Calc Version 1.2 free downloadable software. Energy intake (kcal/kg), refined carbohydrate, fat, and fruit and vegetable intake (% of total intake) will be analyzed as continuous variables and by quartiles.

5.2.4 Anthropometric data will be collected

Body measurements including height and waist-hip ratio and body composition.

A. Waist-hip ratio: Over light clothing with a measuring tape in inches: waist girth (W) is measured at the minimum circumference between the costal margin and the iliac crest; hip girth (H) is measured at the greatest circumference at the level of the greater trochanters. The ratio of W/H is normal for females if less than 0.85.

B. Body composition: Body composition will be estimated by bioelectric impedance analysis performed with a hand-held device (Omrons HBF-360 body Fat Analyzer).

5.2.5 Performance Status based on Karnofsky Scale (Appendix F).

5.2.6 Gail score will be calculated (Appendix D).

Gail score: Age, race, age at menarche, age at first live birth, number of first degree relatives with breast cancer, number of breast biopsies and presence of atypical ductal hyperplasia will be entered into a Gail score calculation program. The resulting score represents a patient's 5-year cumulative risk of breast cancer. A risk greater than 1.66% is the threshold for chemoprevention trials.

5.2.7 Study drug dispensed

Four 250 mg capsules of LEAG will be dispensed for every day of treatment expected (5-14 days) based on the scheduled surgery date.

5.3 Treatment Regimen

5.3.1 Patients will be treated with ginseng for 5 to 14 days prior to surgery. The final dose of LEAG will be administered the day prior to surgery as surgical patients are asked to abstain from food and drink (excluding water) over night prior to surgery.

- 5.3.2 Patients will take four, 250mg tablets daily.
- 5.3.3 Patients will be given a drug diary to record dates of ginseng therapy in order to monitor compliance.
- 5.3.4 Because ginseng has a rare risk of lowering the blood sugar level, patients with diabetes (as defined by the American Diabetes Association) will be encouraged to use their home blood glucose machine to monitor their blood sugar twice a day during treatment and report any readings less than 60. Patients without a home monitoring device will be instructed to report any signs or symptoms of hypoglycemia such as lightheadedness, sweating or confusion. Patients will be provided a diary to track their twice daily glucose checks.
- 5.3.5 Because ginseng has been reported to alter blood pressure and heart rate, patients being treated for hypertension will be encouraged to report any changes of blood pressure greater than 20 mmHg increase from baseline. Patients should be encouraged to have blood pressure readings daily. Patients will be provided with a diary (Appendix I) and a blood pressure monitoring system to record daily blood pressure measurements. If preferred, patients may use their own home monitoring device or use a monitor found at a local drug store.

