3.0 PATIENT SELECTION

3.1 Eligibility Criteria

1. Patients with a cytologically confirmed diagnosis of breast cancer with a biopsy showing invasive or non-invasive breast cancer (DCIS) at least 1.0 cm greatest diameter on imaging (biopsy must have been performed within 6 months of screening visit).
2. Surgical patients, undergoing lumpectomy, subtotal or total mastectomy.
3. Age ≥ 18 years of age.
4. Female.
5. Patients must have tissue blocks available from diagnostic biopsy.
6. Negative pregnancy test, medical history of surgical sterilization, or 1 year post-menopausal. The effects of LEAG on the developing human fetus at the recommended therapeutic dose are unknown. For this reason women of child-bearing potential must agree to use adequate contraception (hormonal or barrier method of birth control; abstinence) prior to study entry and for the duration of study participation.
7. Patient must be willing to forgo surgery for a minimum of 5 days.
8. The ability and willingness to sign a written consent.
9. Patients currently being treated for hypertension must be on a stable dose of medication for the past 30 days.
10. Diabetic patients must be well controlled (HbA1c < 8.5 within past 60 days or documented fasting blood glucose < 140 mg/dl for three consecutive days). Known diabetics who have experienced episodes of symptomatic hypoglycemia in the last 6 months are also considered poorly controlled and will be excluded from study participation.
11. ECOG status of ≤ 2 or Karnofsky $\geq 60\%$ (Appendix F).

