5.4 Interim Phone Call

All patients will be contacted within 48-72 hours by telephone (or in-person if more convenient for patient) of starting medication to assess any adverse events. Any adverse events will be reported to the principle investigator for review and assessment.

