5.5 Day of Surgery Visit

- 5.5.1 Repeat fasting lab work.
- 5.5.2 Obtain tissue samples during scheduled surgery.
- 5.5.3 Review and complete drug accountability and calculate compliance. Collect Ginseng medication diary and any unused study drug.
- 5.5.4 Obtain vital signs.
- 5.5.5 Complete performance status evaluation.

- 5.5.6 Review and complete adverse event log.
- 5.5.7 Review and record concomitant medications.
- 5.5.8 Collect, review and record blood pressure and/or blood sugar diaries (Appendix I), if indicated.

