6.5 Administration Guidelines

Patients will be instructed verbally on the administration of gelatin encapsulated lyophilized water-extract of American Ginseng root.

The study agent will be self-administered in an open-label, unblinded manner to all patients enrolled in the study. During the treatment period, patients will receive 1 gram (4 capsules) of LEAG each day. Capsules should be taken at approximately the same time daily. To reduce the insomnia and hypoglycemic effects, LEAG administration is recommended with breakfast.

Patient must complete at least 5 days of treatment with LEAG prior to day of surgery. LEAG will be dispensed to the patient on the last clinic visit prior to the scheduled date of surgery. Treatment with study medication will be initiated 5 to 14 days prior to surgery and end the night before surgery. **If the patient is not seen in clinic the day that study drug is to be initiated, a reminder telephone call will be made to the patient.** A capsule count will be taken the day of surgery.

Patients will be given a drug diary to record dates of ginseng therapy in order to monitor compliance.

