7.0 Risks/ Precautions

7.1 Contraindications/Precautions

- Ginseng is generally well tolerated when taken orally. Various sources indicate that long term use should be limited to 3 months.
- The most common side effects reported include headache, nervousness/anxiety, sleep disturbances, and gastrointestinal disturbances.
- Estrogenic effects, such as breast tenderness and vaginal bleeding have been reported though not well substantiated.
- Reports of changes in blood pressure and blood sugar levels indicate that individuals being treated for hypertension and/or diabetes should use ginseng with caution.
- Ginseng has been reported to interact with coumadin. Use with coumadin should be closely monitored.

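### Section 5.3.5 warns that ginseng may alter blood pressure but asks treated hypertensive patients to report only a rise, not a fall

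*Combined protocol and SAP*

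**What the plan says.** Section 5.3.5 opens with the reason for monitoring: "Because ginseng has been reported to alter blood pressure and heart rate". Patients on treatment for hypertension are then "encouraged to report any changes of blood pressure greater than 20 mmHg increase from baseline". They are encouraged to take a reading every day and are given a monitor and a diary. Section 7.1 restates the risk, again without a direction: "Reports of changes in blood pressure and blood sugar levels indicate that individuals being treated for hypertension and/or diabetes should use ginseng with caution".

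The provisions around this rule are as follows:

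- **Eligibility.** Section 3.1 item 9 reads "Patients currently being treated for hypertension must be on a stable dose of medication for the past 30 days". Section 3.2 item 11 excludes patients whose pressure is above 140 systolic or 90 diastolic. The criteria set no lower limit.
- **Dosing window.** Section 6.5: "Treatment with study medication will be initiated 5 to 14 days prior to surgery and end the night before surgery".
- **Contact during dosing.** Section 5.4: "All patients will be contacted within 48-72 hours by telephone" of starting the medication, to ask about adverse events.
- **Diary review.** Section 5.5.8, on the day of surgery: "Collect, review and record blood pressure and/or blood sugar diaries (Appendix I), if indicated". Footnote F of the study calendar (section 12.0) also has the diary returned that day.

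**The concern.** The stated risk has no direction, but the trigger has one. The wording is also awkward, because it speaks of any change and then of an increase. It may be a slip for a two-way rule. If so, the text fails to say what was meant. If a one-way rule was intended, no reason is given.

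The rule applies to patients on antihypertensive drugs, the group that section 7.1 marks for caution, in the days before an operation. Section 7.2 adds that the agent may interact with other drugs, again without a direction. A report made during dosing lets the investigator look at the reading and, if need be, stop treatment under section 6.6. A reading first seen on the day of surgery comes too late for that, because the last dose was taken the day before.

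What is at stake is the timeliness of a safety report. Sample size, error rates and the biomarker comparison are not touched.

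**Working it through.** The 20 mmHg limit is a stated clinical trigger and is not derived from other figures in the plan, so there is no figure to reproduce. The check has two parts: a reading of the text, and simple arithmetic on how long and how widely the gap could apply.

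**1. Is a fall covered anywhere?**

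| Place | What it covers | Asks patients to report a fall? |
|---|---|---|
| 5.3.5 | Rise of more than 20 mmHg from baseline | No |
| 5.3.4 (glucose, for comparison) | Readings under 60; symptoms of low glucose if there is no home device | Has a low-side rule, but for glucose |
| 5.4 | One contact at 48 to 72 hours about any adverse event | Not specifically |
| 5.5 | Vital signs, adverse event log and diary on the day of surgery | No; staff review after dosing has ended |
| 7.1 | Caution about changes in pressure | No |
| 11.2 | General adverse event definition, which takes in untoward signs and symptoms | Only if the patient volunteers it |
| Appendix I, consent pages | Not supplied | Cannot be determined |

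The supplied text has one pressure trigger, for a rise, and none for a fall. The paragraph just before it, on glucose, shows that the protocol does set a low-side rule elsewhere.

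**2. How long could a fall wait?**

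Assume time runs from the first dose and surgery follows 5 to 14 days later (section 6.5). The interval from the contact to surgery is days to surgery minus contact time in days.

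- 5-day course: 5 − 72/24 = 2 days; 5 − 48/24 = 3 days.
- 14-day course: 14 − 72/24 = 11 days; 14 − 48/24 = 12 days.
- Overall: 2 to 12 days.

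This is a length of time on the visit schedule. It is not a frequency or a size of harm.

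**3. How many patients does the rule apply to?**

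The documents do not give the number treated for hypertension. Assume 10% to 50% of the 25 to 50 patients in section 16.1.

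- Low end: 0.10 × 25 = 2.5, about 3.
- High end: 0.50 × 50 = 25.

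These are patients covered by the rule, not patients expected to have a fall.

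**4. What reading would a fall of more than 20 mmHg give?**

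- From the highest eligible systolic value: 140 − 20 = 120, so below 120. That is not clinically low.
- From an illustrative baseline of 110, which the criteria allow: 110 − 20 = 90, so below 90.

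The same size of fall can therefore mean very different things, depending on the baseline.

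**The case against.** The best reply is that the point is small and mostly handled elsewhere. Readings are recorded daily, all patients are contacted once early in dosing, adverse events are followed from Visit 1 onward, and the adverse event definition is wide enough to include a fall. The investigator may stop treatment for a change in the patient's condition. Vital signs and the diary are reviewed at surgery. This stands in part: a symptomatic fall has routes to the staff, and the reading itself is not lost. It does not close the gap, because every route open during dosing depends on staff hearing of the fall. A patient told to report rises may reasonably not mention a fall without symptoms.

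A second reply is that a one-sided trigger can be a deliberate choice. The entry rules for these patients also look to the high side, and a rise is a natural sign of lost control. That is possible, but the protocol does not say so, and its stated reason for monitoring is not confined to a rise.

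Third, the unseen sources (the diary form, the consent pages, the Appendix G monograph and the Investigator's Brochure) might give a direction or a low-side instruction. This limits the finding to the supplied text and lowers confidence in it.

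Fourth, a symmetric limit would flag falls that are harmless, such as 140 to just below 120. This is a fair criticism of the simplest fix and is why a different low-side limit should be open to the investigators.

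Finally, the 2018 update revised the objectives according to the data available, so enrolment may have been over. The documents do not settle this. If it was over, the correction would serve only later studies of the agent.

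**Conclusion.** The concern holds on the supplied text. Section 5.3.5 gives a reason with no direction and a trigger for a rise only, and no supplied section asks patients treated for hypertension to report a fall. The remaining gap is an asymptomatic fall, after the 48 to 72 hour contact, that the patient does not volunteer. Staff might not see it until the day of surgery, 2 to 12 days after that contact.

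This is a minor safety correction that should be made. Confidence is medium. The conclusion rests on a literal reading of a sentence that may be a drafting slip, and on the absence of a low-side instruction in the diary form and consent pages. The 3 to 25 patients covered rest on the assumed 10% to 50%. The documents do not show that a fall is the expected direction or how often one would occur.

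**What to change.** Reword section 5.3.5 so that patients report any change from baseline of more than 20 mmHg, whether an increase or a decrease. If the investigators prefer a different limit for a fall, state it. An absolute floor with symptoms to report, on the model of the glucose rule in section 5.3.4, would avoid flagging falls that are not clinically low. The same edit could say whether the limit is systolic or diastolic, which the sentence leaves open. Then check that the blood pressure diary in Appendix I carries the same instruction.

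The cost is one sentence in the protocol and, if the form differs, one line on the diary. The monitor and diary are already supplied, so there is no new data collection. The downside is some additional patient reports, including some caused by home or drug-store monitor error and, under a symmetric limit, some falls that are not clinically low.

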5.4 Interim Phone Call

All patients will be contacted within 48-72 hours by telephone (or in-person if more convenient for patient) of starting medication to assess any adverse events. Any adverse events will be reported to the principle investigator for review and assessment.

5.5 Day of Surgery Visit

- 5.5.1 Repeat fasting lab work.
- 5.5.2 Obtain tissue samples during scheduled surgery.
- 5.5.3 Review and complete drug accountability and calculate compliance. Collect Ginseng medication diary and any unused study drug.
- 5.5.4 Obtain vital signs.
- 5.5.5 Complete performance status evaluation.

- 5.5.6 Review and complete adverse event log.
- 5.5.7 Review and record concomitant medications.
- 5.5.8 Collect, review and record blood pressure and/or blood sugar diaries (Appendix I), if indicated.

